9.2 Sample Size Determination

Approximately 840 participants will be screened to start study intervention in about 420 randomized participants for at least 50 participants evaluable for the primary analysis (i.e. included in the pPPS) per intervention group. The primary analysis will not include the participants enrolled based on visually-confirmed diagnosis, i.e. about half of the women randomized in Japan, nor all the participants randomized in China, who are mainly included to generate further data using the ESD in this population. Refer to Section 9.3 for further information of inclusion of participants into analysis sets.

If blinded data reviews indicate an unexpected high number of screening failures due to the COVID-19 pandemic, enrollment may be increased.

27 JAN 2022 Page: 66 of 99

Sample size calculations were performed for establishing evidence of a drug effect across the doses, that is, detecting a statistically significant dose response signal for the primary efficacy outcome in this study using the MCP-Mod approach. They are based on the following assumptions:

- change in mean EAPP under placebo after 12 weeks of -2.3
- maximum change in mean EAPP of -1.2 for BAY 1817080 over placebo
- standard deviation of 2.5 for all dose groups
- a set of plausible dose-response shapes including Emax and sigmoidal Emax models (chosen based on literature review and historic in-house data)
- random allocation of participants to dose groups according to a 1:1:1:1 ratio,

A sample size of 50 participants per dose groups will have appr. 90% power (averaged across the set of dose-response shapes) to demonstrate a dose- response relationship, using a one-sided test at a type I error rate of α =0.10.

Approximately 70 participants for primary analysis will be randomized to each treatment group to achieve 50 evaluable participants for each treatment group.

In addition, 28 participants from Japan with clinical diagnosis, as well as 28 participants from China will be randomized 1:1:1:1, but will not be included in the primary analysis.

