9.4.3 Secondary Endpoint(s)

For the identification of at least 1 superior effective dose of BAY 1817080 compared to placebo in terms of the absolute change in mean worst EAPP from baseline to end of intervention, pairwise p-values and 80 % as well as 95 % CIs will be derived from an ANCOVA. The mean worst EAPP at baseline and the region (Japan vs. ROW excluding China) are set as covariates.

The secondary endpoint of TEAEs will be analyzed by descriptive statistics, such as frequency tables. A TEAE is defined as any event arising or worsening after the start of study drug administration until 14 days after the last study medication intake. All TEAEs will be tabulated according to the affected system organ class and preferred term, as coded by the

27 JAN 2022 Page: 70 of 99

Medical Dictionary for Regulatory Affairs. Further tables will be provided for serious and/or drug related TEAEs.

Summaries will be provided by intervention group and overall.

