The candidate set of models consists of the $M = 4$ models given by

$$f(d, \theta) = \theta_0 + \theta_1 f^0(d, \theta^0) = -2.3 + E_{max} d^\eta / (ED_{50}^\eta + d^\eta),$$

where d is the dose ranging from 0 mg to 150 mg, θ_0 is a location parameter, and θ_1 is a scale parameter such that only θ^0 determines the shape of the model function, where θ^0 is used to denote parameters associated with $f^0(\cdot)$ component. Guestimates for parameters θ assumed at the trial design stage are listed in Table 1. The two E_{max} models and the two sigmoidal E_{max} models assume a strictly monotonically decreasing dose-response, the illustration of which is provided in the Figure 9–1 in the clinical study protocol.

Table 1: Parameters of the dose-response-curves in the candidate set

Model		Parameters		
Abbreviation	Indicator m	ED_{50}	E_{max}	Hill factor η
emax1	1	25	-1.4	1
emax2	2	100	-2.0	1
sigEmax1	3	35	-1.2	3
sigEmax2	4	75	-1.2	5

Analysis

Step 1: Estimation of μ and S from a mixed model for repeated measures with covariate adjustment

The expected dose response at the tested dose levels will be captured by the adjusted model-based treatment group means of the primary variable's values obtained from a mixed model for repeated measures (MMRM). Absolute change in mean worst EAPP from baseline to each post-baseline time point will be modeled as the dependent variable. The model will include fixed effects for treatment group (four treatment groups: placebo group and 25 mg, 75 mg, and 150 mg BAY 1817080), time point (Visits 3, 4, and 5), time point by treatment group interaction, region (Japan vs. ROW excluding China), and baseline EAPP as continuous covariate. An unstructured variance-covariance pattern will be used to model variance-covariance of the within-subject errors. This variance-covariance matrix will be estimated across treatment groups. In case the model does not converge, alternative variance-covariance structures will be considered. Variance-covariance parameters will be estimated using Restricted Maximum Likelihood (REML) with the Newton-Raphson algorithm and using Kenward-Roger method for calculating the denominator degrees of freedom and adjusting standard errors.

Least squares means for each treatment group at Visit 5 will be estimated from the time point by treatment group interaction term together with their variance-covariance matrix and will represent $\hat{\mu}$ and $\hat{\Sigma}$, respectively. The 80% CIs will also be estimated.

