Absolute change in mean worst EAPP from baseline to post-baseline Visits 3, 4, and 5 may be missing for some participants due to a lack of compliance with eDiary completion. All such missing data and data that are unobservable after IEs intended to be addressed by a hypothetical strategy, as described in the primary estimand definition in Section 6.2.1, will be assumed to be Missing at Random (MAR) and will be modeled as such using the MMRM described above. That is, values of subjects with missing and unobservable data will be assumed to be distributed similarly to subjects with observed data in their treatment group conditional on the covariates included in the model and on partially observed data.

MMRM analysis will be implemented using SAS Proc MIXED.

Step 2: Detection of dose-response signal

For detecting an overall trend, or a dose-response signal, each of the $M = 4$ dose-response shapes in the candidate set will be tested, using a single contrast test.

For each model m in the candidate set

the null hypothesis $H_{0m}: (\mathbf{c}_m)' \boldsymbol{\mu} = 0$

will be tested against

the respective 1-sided alternative hypothesis, $H_{1m}: (\mathbf{c}_m)' \boldsymbol{\mu} > 0$

where $\mathbf{c}_m = (c_{m1}, \dots, c_{mK})'$ is the optimal contrast vector representing model m .

The optimum contrast coefficients and critical values for the four contrast tests on the dose-response shapes will be derived based on the guestimates for parameters $\boldsymbol{\theta}^0$ of standardized versions of the models in the candidate set specified at the design stage, the actual sample size for each treatment group after study completion, and the covariance matrix $\hat{\Sigma}$ estimated from actual data using the MMRM described above [6].

Each dose-response model m will be tested using a single contrast test:

$$T_m = (\mathbf{c}_m)' \hat{\boldsymbol{\mu}} / [(\mathbf{c}_m)' \hat{\mathbf{S}} \mathbf{c}_m]_{m,m}^{1/2}$$

where $[A]_{m,m}$ denotes the m^{th} diagonal element of the matrix A .

The final detection of a dose-response signal is based on the maximum contrast test statistic $T_{max} = \max(T_1, \dots, T_4)$ and can be concluded if $T_{max} > q_{1-\alpha}$, where $q_{1-\alpha}$ is the multiplicity adjusted critical value at level $\alpha = 0.1$. The MCP-Mod method takes multiplicity into account, and no further multiplicity adjustments are needed.

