6.2.2 Secondary efficacy endpoint

The same estimand as the primary efficacy estimand - except the endpoint - will be used for the secondary efficacy endpoints analyses. The IEs a), b) and c) will be handled as described in section 6.2.1.

For the identification of at least 1 superior effective dose of BAY 1817080 compared to placebo in terms of the absolute change in mean worst EAPP from baseline to end of intervention, estimates and CIs will be derived from MMRM. The mean worst EAPP at baseline, the region (Japan vs. ROW excluding China) visit and treatment*visits are set as covariates.

Summaries will be provided by treatment group and overall. Analyses will be performed including the Elagolix population arm.

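### The primary and secondary MMRMs give baseline pain one slope for all three cycles; a baseline-by-time-point term would be a cheap safeguard (minor)

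*SAP*

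**What the plan says.** SAP 6.2.1.1 Step 1 models change from baseline in 28-day mean worst pain at Visits 3, 4 and 5 with an unstructured covariance common to the arms. The fixed effects are treatment, time point, "time point by treatment group interaction, region (Japan vs. ROW excluding China), and baseline EAPP as continuous covariate". Only treatment is crossed with time. The Visit 5 least squares means and their covariance matrix then feed the contrast tests, the curve fit and the minimal effective dose.

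The same model is the only handling of values missing through diary non-compliance, or unobservable after events under the hypothetical strategy. These are taken to be distributed like the observed data of their arm, "conditional on the covariates included in the model and on partially observed data".

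For the secondary comparison, SAP 6.2.2 says: "The mean worst EAPP at baseline, the region (Japan vs. ROW excluding China) visit and treatment*visits are set as covariates". It too has no baseline-by-visit term. Protocol 9.4.3 had planned something else for this endpoint: "pairwise p-values and 80 % as well as 95 % CIs will be derived from an ANCOVA". An ANCOVA at one time point has its own baseline slope.

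No other section adds the interaction. SAP section 7 records that the sensitivity analyses were removed in version 2.0. The documents give no baseline slope, baseline SD or between-cycle correlation.

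**The concern.** The slope of change on baseline at a visit is r × SD(pain at that visit) / SD(baseline) − 1, where r is the correlation of pain at that visit with baseline. Both r and the SD can change over 12 weeks, so equal slopes at Visits 3, 4 and 5 are a restriction. The SAP does not state it as an assumption or justify it.

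If it fails, the fitted slope is a compromise over cycles. At Visit 5 that compromise does two jobs: it adjusts the arm means for chance imbalance in baseline pain, and it helps to predict Visit 5 for women who have only earlier cycles. SAP 5.1 does not automatically exclude dropouts from the per-protocol set, so such women can be in the primary analysis. The first job affects mainly precision. The second can bias a dose-placebo contrast if the women with missing values differ in baseline pain from one arm to another. With the sensitivity analyses gone, nothing remaining in the plan would show whether the restriction matters.

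**Working it through.** **Inputs from the documents.** Protocol 9.2: one-sided α 0.10; "maximum change in mean EAPP of -1.2 for BAY 1817080 over placebo"; "change in mean EAPP under placebo after 12 weeks of -2.3"; SD 2.5; 50 evaluable per dose group from about 70 randomized, a loss of 20/70 = 28.6%. SAP Table 1: the four candidate shapes.

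**Assumed inputs, not in the documents.** Baseline SD 1.5; adjacent-cycle residual correlation 0.75; Visit 3/4/5 slopes from equal (−0.4 throughout) through −0.3/−0.4/−0.5 and −0.2/−0.35/−0.5 to an extreme −0.1/−0.35/−0.6.

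**Step 1: the plan's own figure.** Optimal contrasts for the four shapes, 50 per arm, SD 2.5 and 196 degrees of freedom give a critical value of about 1.53. Power is 89.0%, 89.2%, 93.1% and 90.8%, mean about 90.6%. The stated figure of about 90% is reproduced. It uses no baseline term, so the point here does not touch the sample size.

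**Step 2: complete data.** Leaving region aside, the Visit 5 contrast with a common slope b is

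D = (Ȳ₁₅₀ − Ȳ₀) − b(X̄₁₅₀ − X̄₀),

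where Y is change at Visit 5 and X is baseline. Randomization makes the expected baseline difference zero, so D is unbiased whatever b is. The cost is variance:

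Var(D) = (2/n)[σ² + (β₅ − b)²σₓ²], with σ² = 2.5² − β₅²σₓ².

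- Slopes −0.3/−0.4/−0.5, fitted b = −0.34: (0.16)² × 2.25 = 0.058 against σ² = 6.25 − 0.25 × 2.25 = 5.69. Variance +1.0%, SE +0.5%.
- Slopes −0.2/−0.35/−0.5, fitted b = −0.265: (0.235)² × 2.25 = 0.124 against 5.69. Variance +2.2%, SE +1.1%.
- Slopes −0.1/−0.35/−0.6, fitted b = −0.202: (0.398)² × 2.25 = 0.356 against 6.25 − 0.36 × 2.25 = 5.44. Variance +6.6%, SE +3.2%.

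Large-sample fits (60,000 per arm) agree. The ratio of SEs, common over visit-specific, was 0.4059/0.4040 = 1.005, 0.4066/0.4024 = 1.010 and 0.4059/0.3945 = 1.029.

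**Step 3: about 25% missing at Visit 5, same mechanism in all arms.** Each arm mean shifts by about 0.01 to 0.02 (about 0.04 at the extreme slopes), but the shifts cancel: dose-placebo differences move by 0.006 or less. SE ratios were 0.4388/0.4359 = 1.007, 0.4429/0.4368 = 1.014 and 0.4415/0.4256 = 1.037.

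**Step 4: missingness that depends on baseline differently by arm** (about 65% observed at Visit 5 on placebo, 78% on 150 mg). The 150 mg minus placebo estimate shifts by about −0.06, −0.09 and −0.15 for the three unequal slope sets. With visit-specific slopes there was no systematic shift. The sign follows from the assumed pattern and could reverse.

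**Step 5: finite samples.** 70 per arm, 800 trials per row, critical value 1.53, no Kenward-Roger adjustment. Rejection under the null:

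| Slopes | Missingness at Visit 5 | Common slope | Visit-specific |
|---|---|---|---|
| −0.3/−0.4/−0.5 | MAR, alike in all arms | 12.6% | 13.0% |
| −0.3/−0.4/−0.5 | MAR, differs by arm | 15.0% | 12.5% |
| −0.3/−0.4/−0.5 | about 49%, completely at random | 11.3% | 11.6% |
| −0.1/−0.35/−0.6 | MAR, alike in all arms | 12.6% | 12.8% |
| −0.1/−0.35/−0.6 | MAR, differs by arm | 18.8% | 12.2% |
| −0.1/−0.35/−0.6 | about 49%, completely at random | 10.5% | 11.6% |

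The Monte Carlo SE is about 1.2 points. Both models run above 10% in this simplified set-up, so compare the columns with each other and not with 10%. The excess from the common slope is 15.0 − 12.5 = 2.5 and 18.8 − 12.2 = 6.6 points, and only in the arm-dependent rows. In the completely-at-random rows, power under the emax1 shape was 90.6% against 91.0%, and 90.0% against 91.9%.

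**The case against.** A baseline main effect with unstructured covariance is a legitimate prespecification. Several stronger readings are tempting, and the documents do not support them.

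- **That Visit 5 is adjusted with a wrong slope.** The documents give no slopes. A falling correlation with baseline does not by itself make slopes unequal. With baseline SD 1.6, SD of change 2.5 and r = 0.45 at cycle 3, cycle-3 pain has SD about 2.77 and slope 0.45 × 2.77/1.6 − 1 = −0.22. Cycle 1 with r = 0.6 and SD 2.08 gives 0.6 × 2.08/1.6 − 1 = −0.22 as well. The point is conditional.
- **That the composite rule makes it worse.** Setting change to zero after an adverse-event stop (SAP 6.2.1) multiplies a negative slope by about 1 − p for a fraction p affected. That pulls it towards zero and may offset a slope that grows more negative as correlation decays.
- **That the clinical hold creates bias.** The hold stopped BAY 1817080 and placebo alike, so the missingness it causes should be alike across the arms in this model. In that situation the contrast barely moves.
- **That differential dropout is likely to be left to the model.** The most obvious arm-differential stops, for non-COVID adverse events and lack of efficacy, are imputed. What remains is stops for other reasons and diary gaps. Nothing in the documents says these depend on baseline differently by arm.
- **That the primary model breaks a protocol commitment.** The ANCOVA in Protocol 9.4.3 is for the secondary endpoint. For the primary estimand, Protocol section 3 asks only for means adjusted for region and baseline, and the SAP model provides that.

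All of this stands. It lowers the severity but does not remove the point: the restriction is untested in the one model that drives the primary result, and it is easily lifted.

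**Conclusion.** The restriction is in the text of both models. Its effect depends on conditions that the documents neither establish nor rule out.

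- Slopes equal across cycles: no effect.
- Slopes differ, with data complete or missingness alike across arms: dose-placebo shift of about 0.01 or less and an SE about 0 to 4% larger.
- Slopes differ and missingness depends on baseline differently by arm: a shift of about 0.06 to 0.15 NRS points in the 150 mg contrast, that is 0.06/1.2 = 5% to 0.15/1.2 = 12.5% of the planned maximum effect, with null rejection about 2.5 to 7 points higher.

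These sizes rest on assumed slopes, baseline SD, correlation and dropout pattern. The share of Visit 5 values lost to the early stop is not given either. Severity: minor, a cheap improvement and not a flaw that undermines the primary analysis.

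**What to change.** In SAP 6.2.1.1 Step 1 and in 6.2.2, add the baseline EAPP by time point interaction to the fixed effects. Leave everything else unchanged, including region as a main effect. A region-by-time-point term was not examined in these calculations. It would also rest on few women: Protocol 9.2 plans 28 clinically diagnosed Japanese participants, so if Japan splits about evenly by type of diagnosis, about 28 surgically diagnosed women, or 28/4 = 7 per arm, would enter the primary analysis.

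The cost is one sentence in each section and one term in the PROC MIXED code. Three slopes instead of one use 2 degrees of freedom. If the slopes are in truth equal, the variance of the Visit 5 contrast rises by about 1%. The sample size does not change. SAP 4.6 calls for changes prompted by the data review to be documented before unblinding, and the same timing should apply here.

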4.5 Data Rules

Definition of Baseline

In general, baseline is defined as the last available measurement before start of treatment.

The 28-day baseline period for the ESD items is the last 28 days before start of treatment (e.g. -1 to -28). In case these contain less than 15 available entries, the baseline value will be given by the last 28 consecutive days before the start of treatment with at least 15 non-missing values (e.g. -2 to -29, -3 to -30, -4 to -31 and so on).

In addition, for daily measurements, if baseline and screening periods overlap, all the overlapping measurements will be considered as baseline data.

Definition of Post Baseline

In general, post baseline is defined as the first available measurement after start of treatment. Intervention period is 84 days, capturing 3 menstrual cycles of 28 days on average. As defined in Section 4.3.2, the 28-day mean of an item asking for pain can be derived if at least 15 non-missing entries are available.

Therefore, a post baseline value will be given by 28 consecutive days starting from end of treatment and counting backwards (e.g. day 84 to day 57 will be cycle 3). If a participant does not have 3 full available cycles, the count will start from the last available full cycle with at least 15 non-missing entries available (e.g. if two cycles are available, the count will start from day 56 to 29).

If a participant has 87 days of measurements, the first 3 measurements on day 1,2 and 3 will be discarded.

In addition, if a participant has more than 87 days of measurement, each data collected after day 87 will be discarded.

(Absolute change from) Baseline

To calculate the absolute change from baseline, the baseline value will be subtracted from the post-baseline value of interest, i. e.,

$$\text{Absolute change} = \text{post baseline value} - \text{baseline value.}$$

PROs data rules

If the weekly EIS questionnaire is administered less than 3 days after starting either Week 1, Week 5, 9 or 13 after start of treatment, the collected questionnaires will be counted for the previous 28-day cycle.

For example if a participant has the questionnaire pushed on day 3 after starting her treatment period, the responses will be counted as baseline.

If the monthly EQ5D questionnaire is administered less than 3 days after starting either Week 1, Week 5, 9 or 13 after start of treatment, the collected questionnaires will be counted for the previous 28-day cycle.

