If no candidate model is statistically significant, the procedure stops indicating that a dose-response relationship cannot be established from the observed data. If, on the other hand, there is one or more models with a significant adjusted p value, these significant models will be retained and fitted as described in the next step.

Step 3: Modeling and estimation of target doses

The selected dose-response models (with a significant dose-response trend detected at the previous step) will be fitted to $\hat{\boldsymbol{\mu}}$ and $\hat{\mathbf{S}}$ to estimate the model parameters $\boldsymbol{\theta}$ using a generalized least squares (GLS) estimation criterion [6].

If multiple models have significant adjusted p-values at Step 2 and can be successfully fitted (without convergence or numerical stability issues), final inference will be based on the model with the best fit as determined by the AIC criterion.

To estimate the target dose(s) of interest the minimal effective dose (MED) will be determined:

$$MED = \underset{(d=d_1, d_4)}{\operatorname{argmin}} \{ \tilde{f}(d, \hat{\boldsymbol{\theta}}) > \tilde{f}(d_1, \hat{\boldsymbol{\theta}}) + \Delta \}$$

where $\tilde{f}(d, \hat{\boldsymbol{\theta}})$ is the best estimated model and Δ is the smallest relevant difference, by which a dose is expected to be better than placebo in terms of efficacy measured by the primary efficacy variable.

The MED will be provided for the following smallest relevant differences:

Δ = clinically meaningful threshold (e.g. -1)

Δ = the observed effect of Elagolix in the study

The final choice of the target dose will be based on the analyses of the primary, secondary, and other efficacy variables, as well as safety considerations

MCP-Mod related steps 2 and 3 will be performed using the R “DoseFinding” package (version 0.9-17 or higher) [7].

The level of significance for statistical testing is set to 10 % one-sided. The type I error will be controlled for the primary analysis only.

In consistency with the one-sided level of significance given the generally two-sided reporting of CIs, 80 % CIs will be reported for the primary analysis and its related sensitivity/supplementary analyses in addition to 95 % CIs.

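### The MED formula in Step 3 of the primary analysis has its inequality reversed: with a negative Δ it keeps the doses that fall short of the threshold

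*SAP*

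**What the plan says.** The direction of the endpoint is fixed in SAP 4.5: "the baseline value will be subtracted from the post-baseline value of interest", so improvement is negative. SAP 6.2.1.1 (Assumptions) sets the placebo change at -2.3 and says that the candidate models "assume a strictly monotonically decreasing dose-response".

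In Step 3, "final inference will be based on the model with the best fit as determined by the AIC criterion". The MED is then the smallest d whose fitted value is (in the printed notation) "> \tilde{f}(d_1, \hat{\boldsymbol{\theta}}) + \Delta", that is, above the placebo value plus Δ. Δ is described as the smallest relevant difference "by which a dose is expected to be better than placebo". Two versions are to be used: "Δ = clinically meaningful threshold (e.g. -1" and "Δ = the observed effect of Elagolix in the study". The Step 1 MMRM that feeds Step 3 has "four treatment groups: placebo group and 25 mg, 75 mg, and 150 mg BAY 1817080"; elagolix enters only in the secondary analysis (SAP 6.2.2).

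Protocol 9.4.2 prints the same direction of inequality, on a grid of 25 to 150 mg in steps of 25. It selects the significant model with the highest AIC, asks that the effect at the MED be significant as well as clinically relevant, and leaves the value of Δ to the SAP.

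**The concern.** A dose is better than placebo when its fitted value is lower. With a negative Δ, the placebo value plus Δ is a ceiling that an effective dose should lie below. The printed rule asks for values above it, which contradicts the description of Δ in the same step.

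The MED is the only formal dose estimate in the primary analysis, and protocol 9.1 gives as one aim of that analysis a dose for possible phase III studies. A program that follows the text reports a wrong MED. A program that silently uses the other direction departs from the pre-specified rule.

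Four smaller gaps sit in the same step:

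- The search set is not the same in the two documents.
- The protocol's AIC rule picks the worst-fitting significant model under the usual lower-is-better convention.
- The protocol's significance requirement appears in neither formula.
- The SAP was to define Δ, but leaves the clinical value as an example and does not name the model that supplies the elagolix effect.

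**Working it through.** **Inputs.** Candidate curves (SAP Table 1, protocol Table 9–2) as (ED50, Emax, Hill): emax1 (25, -1.4, 1); emax2 (100, -2.0, 1); sigEmax1 (35, -1.2, 3); sigEmax2 (75, -1.2, 5). From the sample size section: SD 2.5, 50 per group, one-sided α = 0.10, placebo change -2.3.

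**1. The plan's own figure.** Using the curves in their decreasing direction, optimal contrasts at 0/25/75/150 mg, a max-contrast test with 4 × 50 − 4 = 196 degrees of freedom and 1,000,000 simulations, the critical value is 1.527. Power is 89.0%, 89.3%, 93.1% and 90.9%, mean 90.6%. This reproduces the stated 90% or so. The > in Step 2 does no harm, because the contrast coefficients carry the sign (for emax1: 0.797, 0.041, -0.338, -0.500). Step 3 compares fitted values directly and has no such protection.

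**2. Algebra.** For Δ < 0, f(d) > f(d1) + Δ is the same as f(d1) − f(d) < |Δ|, i.e. benefit below the threshold. This holds for any fitted curve.

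**3. Effect over placebo,** e(d) = Emax·d^η / (ED50^η + d^η):

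| Curve | 25 | 50 | 75 | 100 | 125 | 150 mg |
|---|---|---|---|---|---|---|
| emax1 | -0.70 | -0.93 | -1.05 | -1.12 | -1.17 | -1.20 |
| emax2 | -0.40 | -0.67 | -0.86 | -1.00 | -1.11 | -1.20 |
| sigEmax1 | -0.32 | -0.89 | -1.09 | -1.15 | -1.17 | -1.18 |
| sigEmax2 | -0.005 | -0.14 | -0.60 | -0.97 | -1.11 | -1.16 |

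**4. What each rule returns on the protocol grid** (mg; order emax1, emax2, sigEmax1, sigEmax2). The documents give no elagolix effect, so values of Δ other than -1 are assumptions that span a range.

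| Δ | Printed, e(d) > Δ | Reversed, e(d) < Δ |
|---|---|---|
| -0.5 | none, 25, 25, 25 | 25, 50, 50, 75 |
| -0.8 | 25, 25, 25, 25 | 50, 75, 50, 100 |
| -1.0 | 25, 25, 25, 25 | 75, 125, 75, 125 |
| -1.5 | 25, 25, 25, 25 | none for any curve |

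At Δ = -0.5 the printed rule finds no dose on emax1, although every grid dose beats placebo by at least 0.70. The emax2 entry at Δ = -1 is a tie: e(100) is exactly -1.0, so a strict inequality gives 125 and a non-strict one gives 100.

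**5. The SAP search range.** The printed subscript names d1 and d4 and could mean an interval or the tested doses. If placebo is included, it always satisfies 0 > Δ, so the printed rule returns 0 mg at Δ = -1 for every curve. If the interval is open at placebo, it returns doses arbitrarily close to 0. Reversed at Δ = -1, the tested doses give 75, 150, 75, 150. On a continuous range the crossing is d = ED50·[x/(1−x)]^(1/η) with x = Δ/Emax:

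- emax1: 25 × 2.5 = 62.5
- emax2: 100 × 1 = 100
- sigEmax1: 35 × 5^(1/3) = 59.85
- sigEmax2: 75 × 5^(1/5) = 103.5

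**6. Other readings.** If f were sign-reversed with Δ = -1, placebo would qualify. If Δ were +1 on the stated scale, no dose on a decreasing curve would qualify. Nothing in either document reverses a sign before Step 3.

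All doses above only show what the formula returns; none is a proposal.

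**The case against.** The algebra is hard to dispute; the case against is about weight and about the smaller points.

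- **Reach.** Amendment 2 stopped treatment and enrolment, protocol 2.3.3 no longer regards the benefit-risk ratio as positive, and SAP section 7 records early termination of project and study. The use of the MED for phase III planning has largely gone. The MED is computed only after a significant Step 2, and the final dose choice also weighs other data. This stands and limits the severity.
- **Text, not result.** The meaning of Δ is plain, Step 3 runs in a named R package, and a programmer who obtained placebo as the MED would probably notice. The documents therefore show a wrong specification and not a wrong result. This also stands.
- **Search set.** The SAP subscript is unclear, so how far it differs from the protocol grid is uncertain. It still needs one clear statement.
- **Significance.** The protocol's wording can be read as the Step 2 gate. A dose-level reading is possible but not forced, so this is a request to clarify.
- **AIC and elagolix.** The SAP's best-fit wording governs in practice, and the MMRM in SAP 6.2.2 is the evident source of the elagolix effect. Neither fact corrects the protocol or names the source in Step 3.
- **Illustration.** The figures rest on design-stage guesses, whereas the rule applies to fitted curves. True, but step 2 of the working does not depend on the curve.

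**Conclusion.** The concern holds and should be fixed. As written, for any negative Δ the MED rule keeps doses whose benefit is below the threshold and excludes those that reach it. At Δ = -1 it gives 25 mg on the protocol grid for all four design curves, where the benefit is 0.005 to 0.70 of the required 1 point, or placebo if placebo is in the search set. The direction of the error follows from the plan's own definitions alone. Its numerical size assumes the design-stage curves, and for the elagolix version that Δ means elagolix minus placebo and is negative.

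The dose-response test, the power and the secondary estimates are untouched. What is at stake is the correctness of a reported primary-analysis estimate: SAP version 3.0, issued to correct typos, still contains Step 3. The protocol's AIC wording is also wrong as written. The search set, the significance wording, the open clinical threshold and the unnamed elagolix model are clarifications.

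**What to change.** In SAP 6.2.1.1 Step 3, and in protocol 9.4.2 if it is amended:

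- Write, for negative Δ, MED = min{d > d1 : f(d, θ̂) < f(d1, θ̂) + Δ}, equivalently f(d1) − f(d) > |Δ|, and state whether the inequality is strict.
- Use one search set that reconciles the SAP range with the protocol's 25 mg grid, with placebo excluded. For negative Δ the reversed rule already excludes placebo; the explicit exclusion matters if the observed elagolix effect is not negative.
- Report that there is no MED in range when no dose qualifies.
- Keep both versions of Δ. The sponsor should fix the clinical threshold in place of an example, name the model that supplies the elagolix-minus-placebo effect, and say what is reported if that effect is not negative.
- In the protocol, change the highest AIC to the lowest. Either drop the significance requirement from the MED wording or add it as a condition with a stated confidence level; both documents link the two-sided 80% interval to the primary analysis.

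The cost is a text correction and a check that the program computing the MED uses the intended direction. No data collection and no participant is affected.
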